7. DATA COLLECTION

Health facility survey: This anonymous survey will be administered to a health facility manager at baseline to capture facility characteristics (number of staff, patient demographics, services provided, etc.), including turnover of SP-trained HCWs, patient volume, and any relevant changes in HIV policies and procedures.

Unannounced SP checklist: A survey will be completed by each SP actor, following every clinical interaction with an HCW provider using electronic tablets. The surveys will be conducted at baseline and after the HCW training at all 24 sites. The tool will assess domains of counseling and communication skills, and adherence to national PrEP guidelines.

SP training checklist: Standardized SP checklists will be used to evaluate the HCW encounter with the SP actor. The SP will complete checklists based on individual scenarios to provide feedback for the HCW on their practice session and provide a score based on competencies met.

HCW surveys: HCW participants will complete surveys prior to and after the SP training to assess knowledge of and self-rated competency in provision of PrEP to AGYW, beliefs about AGYW and HIV, and basic demographic and work information.

HCW training evaluation surveys: Post-training surveys will be administered to HCW participants to obtain feedback on the quality, length, and relevance of the SP training.

8. STATISTICAL CONSIDERATIONS

8a. Sample Size and Power

Given a fixed number of clusters (24 facilities), we estimated the minimum number of SP encounters required to detect a 20 percentage-point difference in PrEP counselor competency score between intervention and control arms. Because it is uncertain what baseline PrEP competency would be, we estimated sample sizes to detect a 20-percentage point difference between the intervention and control arm varying the baseline competency percent, shown in Table 2 (following page). Under these assumptions, if PrEP competency is 20% in the control arm, we would need an estimated 192 total SP encounters (8 per site). Higher baseline competency would require a larger sample size to detect the same difference. Given this range, and logistical constraints of larger samples with this type of evaluation, the expected upper limit of SP encounters is 400.

Table 2. Sample sizes of SP encounters to detect a 20% difference in competency at 80% power, correlation coefficient (k) of 0.15, $\alpha=0.05$ and 24 facilities

Control group competency %	Intervention group competency %	Cluster per arm (fixed)	SP encounters per cluster	Total SP encounters
0.2	0.4	12	8	192
0.3	0.5	12	10	240
0.4	0.6	12	11	264
0.5	0.7	12	12	288
0.6	0.8	12	13	312
0.7	0.9	12	30	720

8b. Analysis Plan

A CONSORT diagram will be used to show the number of facilities and HCWs by arm during the trial, numbers excluded, and reasons for exclusion. Baseline characteristics of each facility by intervention arm will be presented as descriptive statistics to assess whether balance of these factors was achieved through randomization using t-tests and McNemar's exact tests for continuous and dichotomous variables.

An intention-to-treat (ITT) analysis will be used to evaluate whether the SP training intervention resulted in higher competency scores at intervention compared to control facilities. The primary outcome will be at the individual level, adjusted for relevant baseline characteristics by arm and baseline evaluation scores. Generalized linear models (GLMM) with a Poisson distribution and log link, will be used to estimate rate ratios, and accounting for facility cluster as a random effect. Secondary analysis will be conducted using a similar GLMM modeling approach with provider overall communication quality score percent as the outcome. In addition, we will evaluate the intervention effect on individual components of PrEP competency and communication quality in separate GLMM regression models.

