4. STUDY DESIGN

During the first phase (Aim 1) we will conduct a cross-sectional baseline assessment of PrEP counseling practices using unannounced SP actors as evaluators. SP actors are trained professional actors recruited from a Kenyan casting agency. They will be paid study staff, managed by our Study Coordinator. Before the study, actors will be trained in the SP methodology based on the study protocol. All SP actors will sign a confidentiality agreement and complete protection of human participants training before any contact with participants. Based on this assessment, we will develop and implement a clinical training program utilizing SP actors to improve adherence to national guidelines and communication skills. Finally, we will evaluate the training program through a parallel cluster-randomized trial of the SP training using repeat unannounced SP encounters at 24 health facilities purposively selected from all facilities in Western Kenya offering PrEP (Aim 2).

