5. STUDY ENROLLMENT

5a. Population and Setting

The study will be implemented in 24 large public health facilities that provide PrEP care and counseling services to AGYW in Kisumu and other counties in Western Kenya. The facilities were purposively selected by the study team from among all facilities offering PrEP (37) based on factors such as size, location, and receptiveness of the facility to host research. The purposively selected study sites are: Chiga, Chulaimbo, Manywanda, Muhoroni, Nyalenda, Awasi, Koru, Ahero, Rabour, Lumumba, KCH, Migosi, Nightingale, Airport, Maseno, Bar Korwa, Railway, Rata, Nyan'goma, Nyalunya, Nyangande, Sondu, Ober-Kamoth, and Ojolla. At each site, the study will include HCWs who provide HIV care and PrEP services for AGYW. Inclusion and exclusion criteria are shown in Table 1, below.

5b. Eligibility criteria

Health Facility: Eligible facilities will include public health facilities that offer PrEP services and counseling to AGYW located within Western Kenya. Facilities with ongoing PrEP interventions where study staff will be excluded.

HCW participants: Eligible HCWs will be 18 years or older, current employees of one of the 24 facilities in the study, provide PrEP services to AGYW, and be able to provide informed consent. In Kenya, HCWs who provide PrEP therapy and counseling are most commonly trained nurses. The nurses are specifically trained in delivering PrEP per NASCOP guidelines.

Table 1. Inclusion Criteria

Population	Selection	N	Inclusion Criteria	Exclusion Criteria
Health Facilities	Facilities in Western County providing PrEP services for AGYW	24	Located in a county in Western Kenya Currently offering PrEP services	Sites where PrEP services are staffed by study staff
HCWs at selected facilities	HCWs working in any of the selected health facility sites	Up to 240	Age 18 or over Able to provide consent Current employee of one of the 24 selected facilities Currently providing PrEP services	Study staff seconded to the site as part of a trial or intervention

5c. Randomization

Randomization will occur at the cluster level: 24 facilities will be purposively selected from a list of all facilities in Western Kenya with PrEP services. We will use stratified randomization, through which 12 facilities will be allocated to the intervention and 12 will be assigned standard of care according to facility size, to ensure balance by arm. A UW biostatistician will generate the randomization assignment for each clinic.

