Primary outcome: Provider competency score using the endline unannounced SP checklist, expressed as a mean %, at the individual level. Each provider will receive a total score (% correct) from the checklist, rescaled to be out of 100.

Computing the total score per provider:

- The unannounced SP checklist contains 12 questions on adherence to PrEP guidelines with binary (done/not done) response options and 7 items on communication quality with 4 scaled response options (strongly agree to strongly disagree). Higher total scores represent higher competency.
- Each binary response option will be assigned 1 for 'done' and 0 for 'not done' for a total possible sub-score of 12.
- Communication items number #4, and 6-10 will be scored 3=strongly agree, 2=agree, 1=disagree, 0=strongly disagree. Question #5 is reverse coded (it is a negative question) as 3=strongly disagree, 2=disagree, 1=agree, 0=strongly agree, for total possible sub-score of 21.
- Each domain score will be converted a percentage of points possible. Total scores will be computed by adding the converted percentages and dividing by 2 (the number of domains), so that each domain is weighted equally.

Exposure: 12 Facilities that received the SP training intervention compared to 12 facilities without the SP intervention.

Adjustment variables: Pre-specified facility size/level, any baseline factors that differ between arms at $p<0.05$ level in addition to the primary exposure (intervention v. control) and stratification variables.

Clustering: Individuals within facilities

Data sources: HCW surveys, Facility survey, unannounced SP actor checklists

Primary analysis of trial endpoints: Primary analysis will be intention-to-treat (ITT).

[figure not shown]
A CONSORT diagram will be used to show the number of facilities and HCWs by arm during the trial, numbers excluded, and reasons for exclusion (Figure 1).

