- Descriptive statistics, including means, medians, and proportions of data from baseline surveys and SP checklists will be generated including facility size, staffing, HCW age, gender, PrEP training exposure, and years providing HIV prevention services (Table 5). Baseline unannounced SP checklist scores will be presented as mean %. These data will be presented by trial arm in Table 1 to determine whether randomization achieved balance by potential confounding factors. Chi square and ranksum tests will compare differences in categorical and continuous variables by arm. Variables that differ between arms at the $p<0.05$ will be included *a priori* in the regression model.
- An intention-to-treat (ITT) analysis will be used to evaluate whether the SP training intervention resulted in higher mean competency score % at intervention compared to control facilities. The primary outcome will be at the individual level, adjusted for relevant baseline characteristics by arm and baseline evaluation scores. Generalized linear models (GLMM) with a Gaussian distribution and identity link, will be used to the difference in mean score %s between the intervention and standard of care facilities, accounting for facility cluster as a random effect (Table 6). We will consider individual SP as another random effect.

- In sensitivity analyses, we will evaluate the intervention effect on individual components of PrEP competency and communication quality in separate GLMM regression models as well as differences in overall mean % scores between cases, where case is entered as a fixed effect (a covariate).

Data sources: HCW surveys, Facility Surveys, Unannounced SP checklists, Exit Surveys

Figure 1. PrIYA-SP CONSORT diagram

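### Protocol 8b names a paired test (McNemar) for unpaired facilities, and the SAP lets HCW-level balance tests with no stated allowance for facility clustering add covariates to the primary model

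*Protocol*

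**What the plan says.** **Protocol.** Section 8b works at facility level: "Baseline characteristics of each facility by intervention arm will be presented as descriptive statistics", with balance assessed "using t-tests and McNemar's exact tests for continuous and dichotomous variables". The design in section 4 is parallel: "we will evaluate the training program through a parallel cluster-randomized trial". Section 5c reads "We will use stratified randomization, through which 12 facilities will be allocated to the intervention and 12 will be assigned standard of care", with facility size as the stratifier. Neither document mentions matched pairs. Section 8b adjusts the primary outcome for relevant baseline characteristics and baseline scores, and ties no p-value to that choice.

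**SAP.** The descriptive bullet under the primary analysis changes the tests: "Chi square and ranksum tests will compare differences in categorical and continuous variables by arm". The variables it lists include HCW age, gender, PrEP training exposure and years of service. It then adds a consequence: "Variables that differ between arms at the $p<0.05$ will be included" in the regression model. The adjustment-variables entry repeats the rule as "any baseline factors that differ between arms at $p<0.05$ level", alongside facility size/level and the stratification variables. Baseline scores are also adjusted for. The SAP acknowledges the data structure, "Clustering: Individuals within facilities", and gives the outcome model a facility random effect. It says nothing about clustering for the balance tests.

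**The concern.** There are two separate faults.

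First, McNemar's test compares the discordant cells within pairs. Twelve facilities in one arm and twelve different facilities in the other form no pairs, so the test is undefined for the comparison that Protocol 8b describes.

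Second, HCWs at one facility are likely to resemble each other in cadre, training and experience. A chi-square or rank-sum test on individual HCWs treats them as independent and declares imbalance too often. Under the SAP this has a consequence, because each declared imbalance puts a covariate into the primary model. What is at stake is a primary model whose covariates depend partly on mis-sized tests, with only 24 facilities to support them.

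**Working it through.** **Inputs.** 12 v 12 facilities (Protocol 5c). About 10 HCWs per site (Protocol 5d): 24 × 10 = 240, which reproduces the stated total. HCW-level rows of SAP Table 5: sex, age, cadre, years of experience and prior training, so five. The other rows, including three labelled as facility mean scores, are facility-level; I count 13 from a table damaged in extraction. Two-sided tests are assumed. The documents' 0.15 refers to the competency score, not to HCW characteristics, so the ICC is varied.

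**1. McNemar on unpaired facilities.** Suppose a characteristic is present in 9/12 v 3/12 facilities. Any pairing gives discordant counts (b, c) with b − c = 6. The exact p is 2 × Σ(i=0 to c) C(b+c, i) / 2^(b+c).

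| Pairing (b, c) | Exact p |
|---|---|
| (6, 0) | 2 × 1/64 = 0.031 |
| (7, 1) | 2 × 9/256 = 0.070 |
| (8, 2) | 2 × 56/1024 = 0.109 |
| (9, 3) | 2 × 299/4096 = 0.146 |

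The same data fall on either side of 0.05 according to an arbitrary pairing. Fisher's exact test gives one answer: 2 × (48,400 + 4,356 + 144 + 1) / 2,704,156 = 0.039.

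**2. True size of an HCW-level test that ignores facility.** Design effect DE = 1 + (m − 1) × ICC; size ≈ 2 × [1 − Φ(1.96/√DE)]. The approximation was checked with 20,000 simulated trials of 24 × 10 HCWs and no true difference (beta-binomial data for chi-square, normal data for rank-sum).

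| Assumed ICC | DE, m = 10 | Approx. size, m = 10 | Simulated chi-square | Simulated rank-sum | Approx. size, m = 5 |
|---|---|---|---|---|---|
| 0 | 1.00 | 5.0% | 4.4% | 5.0% | 5.0% |
| 0.01 | 1.09 | 6.0% | 5.4% | 6.3% | 5.5% |
| 0.05 | 1.45 | 10.4% | 9.7% | 9.9% | 7.4% |
| 0.10 | 1.90 | 15.5% | 14.9% | 15.5% | 9.8% |
| 0.15 | 2.35 | 20.1% | 19.8% | 19.5% | 12.1% |

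**3. Covariates selected by chance.** The expected number is the sum of the sizes and needs no independence between rows.

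- Five HCW rows: 5 × 0.05 = 0.25 at the nominal level, 5 × 0.104 = 0.52 at ICC 0.05, and 5 × 0.201 = 1.0 at ICC 0.15.
- All 18 rows at a true 5%: 18 × 0.05 = 0.9.
- All 18 rows with the HCW rows at 20.1%: 13 × 0.05 + 5 × 0.201 = 1.7.
- If rows were independent, the chance of at least one selection would be 1 − 0.95^18 = 60%, rising to 1 − 0.95^13 × 0.799^5 = 83%.

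One of the 13 facility-level rows is baseline competency, which enters anyway; without it, 1.7 becomes 1.6.

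**4. Effect on the primary test.** A facility-level regression was used as a proxy: 24 facilities, no treatment effect, the 18 candidates above, ICC 0.15, selection at p<0.05, 1,500 runs per setting (Monte Carlo standard error √(0.05 × 0.95/1500) ≈ 0.6 percentage points).

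| Candidates | Tests on HCW rows | Mean covariates selected | Type I error |
|---|---|---|---|
| Not prognostic | ignore facility | 1.67 | 5.5% |
| Not prognostic | facility means | 0.87 | 5.0% |
| Two prognostic | ignore facility | 1.70 | 4.5% |
| Two prognostic | facility means | 0.91 | 4.1% |

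Naive testing roughly doubles the number of covariates selected, but the primary test stays near its nominal level. The proxy uses t-tests in place of the SAP's tests, and leaves out the baseline score and the strata.

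**The case against.** The case for leaving this alone has several parts, and most of them stand.

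- A reader might infer that the p-values of both documents choose covariates. The documents do not support that. The Protocol has no p-value rule, and the SAP, dated September 2021 against May 2019 for the Protocol, has already dropped McNemar's test. What remains in Protocol 8b is a wording error.
- The tests are not wrong throughout. T-tests on 12 v 12 facilities are legitimate, and chi-square and rank-sum tests suit the facility rows and the three facility-mean rows of SAP Table 5. The one caveat is small counts: for 9/12 v 4/12, uncorrected chi-square gives p = 0.041 and Fisher's exact test gives 0.100.
- SAP Table 5 has no p-value column, so balance is to be displayed descriptively. The tests matter only through the selection rule.
- The SAP does not state the unit of analysis for the HCW rows. Treating HCWs as independent is the natural reading of the tests it names, but it is a reading.
- Facility size/level, stratification variables and baseline scores enter the model regardless, so the p-values choose only additional covariates.
- The ICC is unknown. At 0.01 the distortion is negligible, and with five HCWs per facility it is smaller throughout.

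None of this removes the gap. The SAP recognises clustering for the outcome model, says nothing about it for the tests that feed that model, and calls the data-driven rule a priori.

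**Conclusion.** Both faults are real and limited. McNemar's test is unsuitable in Protocol 8b, but selects nothing as documented. In the SAP, five HCW rows would be tested with no stated allowance for facility. Their true size would be about 6% to 20% for ICCs of 0.01 to 0.15 with 10 HCWs per facility, and about 5.5% to 12% with five. This assumes equal cluster sizes, two-sided tests and testing at HCW level.

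A reader might go on to infer that the primary test is invalid or its estimate biased. Nothing here shows that: type I error was 4.5% to 5.5% after naive selection in the proxy. The demonstrated cost is a covariate set driven more by chance, an unfixed primary model, and lost degrees of freedom among 24 facilities. Correcting the tests alone would still leave about 0.9 chance selections expected over 18 rows, so the p<0.05 rule itself is the larger weakness. Severity: minor to moderate.

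**What to change.** 1. **Protocol 8b:** delete McNemar's test. If a test of dichotomous facility characteristics is kept, name Fisher's exact test.
2. **SAP, descriptive bullet:** describe the HCW rows by arm without tests. If tests are wanted, compare facility-level summaries or use a model with a facility random effect. State that no p-value ignoring facility is used to choose covariates.
3. **SAP, adjustment variables (preferred):** replace the p<0.05 rule with a set fixed before endline scores are compared by arm: facility size/level as the stratifier, the baseline score, and any further covariates by name. Balance can then be shown with summary statistics or standardised differences.

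The cost is about one sentence in each document and trivial programming. No data collection or sample size changes.

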9. DATA MANAGEMENT

A dedicated data team will be responsible for the entry, management, and monitoring of study data, in accordance with standard operating procedures. The Nairobi data team will communicate frequently with the Seattle-based statistical team for reporting, data cleaning, study monitoring, and interim analyses. Study data will be uploaded to the secure study cloud server using REDCap. REDCap is a secure, web-based application designed to support data capture and management for research studies. The software provides 1) an intuitive interface for validated data entry; 2) automated export procedures for seamless data downloads; and 3) procedures for importing data from external sources.

9a. Data Capture and Storage Methods

Video-recordings: Videos from HCW participants in SP training who have consented to allow their videos to be used for further training purposes will be stored on a secure server for at least three years after completion of the study by the University of Washington.

Surveys and unannounced SP checklist: Health facility surveys and the unannounced SP checklist will be administered by study staff via electronic tablets using REDCap data collection software and uploaded daily during survey capture periods. Data will be transported via secure socket layer (SSL) and only accessible by authenticated users. Weekly reports will be generated to monitor study progress and troubleshoot problems. All computers, tablets, and individual study databases will be encrypted, and password protected.

SP training checklist: Data from the checklist will be shared with the HCW during the training session. The original paper copies of the checklist will be identified using a study ID number. They will be stored in a secured locked cabinet in a study office accessible only to study staff.

Data Custody and Retrieval: All data for this study will be under the custody of the Principal Investigators, Site PI, and authorized study staff. Data retrieval procedures will be similar for all types of data in this study. Authorized study staff members will download the datasets from the secure servers for routine quality checking and analyses. All downloaded data will be maintained on a secured, password-protected study computer. From these data sources, the analysts will create merged datasets for planned analyses.

Study Records Retention: Retention of study records will comply with UW, KNH, and federal requirements (<http://f2.washington.edu/fm/recmgt/retentionschedules/gs/general/uwgsResearch#Research>). All consents, study data and link between HCW participant identifiers and study ID codes will be retained following completion of the study for a period of time in accordance with UW and KNH requirements.

Data handling procedures: Members of the research team have completed required training in human subjects, including training in data handling and confidentiality. All data for this study will be under the custody of the Principal Investigators, Site Leader, and authorized study staff.

Security of electronic records: To protect participant identity, all data will be stored on password protected computers, accessible only to the study staff. Authorized study staff members will download the datasets from the secure servers for routine quality checking and analyses. All downloaded data will be maintained on

a secured, password-protected study computer. From these data sources, the analysts will create merged datasets for planned analyses.

10. ASSESSMENT OF SAFETY

10a. IRB monitoring

The IRB at the University of Washington (UW) and at the Kenya National Hospital Ethics Review Committee (KNH ERC). Will periodically review the study protocols and maintain ongoing oversight of the risks and benefits of the study and ensure compliance with institutional guidelines. Monitoring of adverse events will be done by PI and project staff and any problems will be recorded in a study database. Research and clinical staff will be trained to identify potential adverse events and instructed to report them immediately to the site PIs and in-country research director.

10b. Reporting adverse events or unanticipated events

In compliance with federal regulations and UW policy, the Principal Investigator will notify the UW Human Subjects Division (HSD) and or UW Institutional Review Board (IRB), Kenyan Ethics Committee, and relevant local Kenyan authorities (i.e. Ministry of Health) of any unanticipated problems within 10 business days. Adverse events and study procedure-specific adverse events are expected to be rare in this clinical training intervention. If any occur, they will be reported to the UW IRB and KNH ERC within 24 hours. Any breach or possible breach of confidentiality of any participants in this study will be reported to UW HSD and/or IRB within the timeframe established by these ethics committees.

10c. Potential adverse events and mitigation

Answering questions: We may ask questions that make participants feel embarrassed or uncomfortable. Some questions are about their beliefs, attitudes, and perceptions of providing counselling to AGYW about sexual history and health. In addition, provider participants in the intervention arm may feel discomfort sharing their views and training experiences during the group debriefing sessions.

To minimize the risk of embarrassment, participants will be reminded that they can choose whether to answer any question. Participant answers will be confidential. Participants in the training intervention will be assured that it is a safe and non-judgemental space to share their views and experiences.

Loss of Confidentiality: Others may learn that a participant is part of the study. We have procedures in place to protect confidentiality and will do everything possible to reduce this risk. HCWs who have consented to the study may be video recorded during SP encounters that take place in the training. There is a chance that others could find out about participants through these recordings. However, each SP training participant will have the opportunity to sign a waiver to allow use of the SP encounter video footage outside of the study (e.g., dissemination activities, examples for future SP trainings, online courses, conference presentations). Videos containing footage of any participant who has not signed the waiver will not be used outside of the training.

We will keep participant identity as research subjects confidential. Responses to questions will be kept private. No identifying information or any kind will be released to any other person or agency that is not working on this study without participant permission in writing. We will not publish or discuss in public anything that could identify participants. All of their information, including the link between participant name and code number will be kept in a secure location at the clinic only. Once the study is completed, we will maintain the link following Kenyatta National Hospital and University of Washington guidelines, after that period we will remove their name and all identifying information from the study files. Any publications of this study will not use their name or identify participants. All of the information will be confidential. However, if we learn that they intend to harm themselves or others, we must report that to the authorities. Although we will make every effort to

keep their information confidential, no system can be completely secure. It is possible that someone could find out a participant was in this study and could find out information about them.

10d. Study oversight

The trial data safety monitoring plan will be overseen by the Principal Investigators, Drs. [name] and [name]. An external oversight committee, appropriate to the level of risk for a trial of a training intervention, will be convened and meet regularly according to written procedures to monitor recruitment, enrollment, adherence to protocol, and any potential social harms. The external committee will consist of experts in adolescent HIV prevention and treatment research and clinical practice. All program activities will be implemented through the standard routine PrEP clinical process. The protocol, data collection tools, and consent forms will be reviewed and approved by the UW IRB and the KNH ERC.

